4.4 Exclusion Criteria

The subject must be excluded from participating in the trial if the subject:

1. Is currently participating in a study of an investigational agent and received an investigational agent within 4 weeks of the first dose of treatment on this protocol
2. Has received any immunotherapy agents outside of this protocol within 4 weeks of the first dose of treatment on this protocol

3. Has a diagnosis of immunodeficiency or is receiving chronic systemic steroid therapy (>10 mg of prednisone daily or equivalent) or any other form of immunosuppressive therapy within 14 days prior to the first dose of study drug.
4. Has a known history of active TB infection (*Bacillus tuberculosis*)
5. Has active COVID-19 infection
6. Has known history of, or any evidence of active, non-infectious pneumonitis that required steroids, or active pneumonitis
7. Has a severe hypersensitivity to nivolumab or any of its excipients
8. Has a severe hypersensitivity to ipilimumab or any of its excipients
9. Has an active autoimmune disease that has required systemic treatment in the past 2 years (i.e. with use of disease modifying agents, corticosteroids or immunosuppressive drugs)
10. Has a known additional malignancy that is progressing or required active treatment within the 3 years prior to enrollment - exceptions include basal cell carcinoma of the skin or squamous cell carcinoma of the skin that has undergone potentially curative therapy or in situ cervical cancer or other tumors that will not affect life expectancy
11. Has an active infection requiring systemic therapy
12. Has a known history of HIV, Hepatitis B, or Hepatitis C
13. Has known psychiatric or substance abuse disorders that would interfere with cooperation with the requirements of the trial.
14. Is pregnant or breastfeeding, or expecting to conceive or father children within the projected duration of the trial, starting with the screening visit through 120 days after the last dose of trial treatment
 - a. Female subjects of childbearing potential should have a negative urine or serum pregnancy within 72 hours prior to receiving the first dose of study medication. If the urine test is positive or cannot be confirmed as negative, a serum pregnancy test will be required.

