 - b. Female subjects of childbearing potential should be willing to use 2 methods of birth control or be surgically sterile, or abstain from heterosexual activity for the course of the study through 120 days after the last dose of study medication (Reference Section 5.8.2). Subjects of childbearing potential are those who have not been surgically sterilized or have not been free from menses for > 1 year.

- c. Male subjects should agree to use an adequate method of contraception starting with the first dose of study therapy through 120 days after the last dose of study therapy.
- 15. Is on anticoagulation that cannot be discontinued in the perioperative period
- 16. Has received a live vaccine within 30 days of planned start of study therapy

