4.7 Discontinuation of Study and Participant Withdrawal

Discontinuation of study intervention does not represent withdrawal from the study. As data on clinical events beyond study intervention discontinuation may be important to the study, they must be collected through the participant's last scheduled follow up, even if the participant has discontinued study intervention. Therefore, all participants who discontinue study intervention prior to completion of the protocol-specified treatment period will still continue to participate in the study.

Participants may discontinue study intervention at any time for any reason or be discontinued from the study intervention at the discretion of the investigator should any untoward effect occur. Also, a participant may be discontinued from study intervention by the investigator if study intervention is inappropriate, the study plan is violated, or for administrative and/or other safety reasons. A participant must be discontinued from study intervention but continue to be monitored in the study for any of the following reasons:

1. The participant or participant's legally acceptable representative requests to discontinue study intervention.
2. Any occurrence of another malignancy that requires treatment.
3. Unacceptable AEs or toxicities
4. The participant interrupts study intervention administration for >28 consecutive days
5. The participant has a medical condition or personal circumstance which, in the opinion of the investigator, placed the participant at unnecessary risk from continued administration of study intervention.
6. The participant has a confirmed positive serum or highly-sensitive urine pregnancy test.

A participant must be withdrawn from the study if the participant or participant's legally acceptable representative withdraws consent from the study. If a participant withdraws from the study, they will no longer receive study intervention or be followed at scheduled protocol visits.

Lost to Follow-up

If a participant fails to return to the clinic for a required study visit and/or if the site is unable to contact the participant, the following procedures are to be performed:

1. The site must attempt to contact the participant and reschedule the missed visit. If the participant is contacted, the participant should be counseled on the importance of maintaining the protocol-specified visit schedule.

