6.6.2 Contraception

Nivolumab and ipilimumab may have adverse effects on a fetus in utero. Furthermore, it is not known if nivolumab or ipilimumab have transient adverse effects on the composition of sperm. Non-pregnant, non-breast-feeding women may be enrolled if they are willing to use 2 methods of birth control or are considered highly unlikely to conceive. Highly unlikely to conceive is defined as 1) surgically sterilized, or 2) postmenopausal (a woman who is \geq 45 years of age and has not had menses for greater than 1 year will be considered postmenopausal), or 3) not heterosexually active for the duration of the study. The two birth control methods can be either two barrier methods or a barrier method plus a hormonal method to prevent pregnancy. Subjects should start using birth control from study Visit 1 throughout the study period up to 120 days after the last dose of study therapy.

The following are considered adequate barrier methods of contraception: diaphragm, condom (by the partner), copper intrauterine device, sponge, or spermicide. Appropriate hormonal contraceptives will include any registered and marketed contraceptive agent that contains an estrogen and/or a progesterone agent (including oral, subcutaneous, intrauterine, or intramuscular agents).

Subjects should be informed that taking the study medication may involve unknown risks to the fetus (unborn baby) if pregnancy were to occur during the study. In order to participate in the study, they must adhere to the contraception requirement (described above) for the duration of the study and during the follow-up period. If there is any question that a subject will not reliably comply with the requirements for contraception, that subject should not be entered into the study.

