7.0 TRIAL PROCEDURES

7.1 Flow Chart – Schedule of Events

7.1.1 Flow Chart for Screening, Neoadjuvant, and Surgery Phases

Table 2. Trial Flow Chart of Screening, Neoadjuvant, and Surgery Phases

Trial Phase:	Screening Phase	Neoadjuvant Treatment Phase		Pre-Surgery Phase	Surgery Phase	Post-Surgery Recovery Phase
	Screening (Visit 1)	C1 D1	C1 D22C	4 Weeks	3 Weeks	3-4 Weeks
Scheduling Window (Days):	-28 to -1		± 3			
Administrative Procedures						
Informed Consent	X					
Inclusion/Exclusion Criteria	X			X	X	
Demographics and Medical History	X			X	X	
Prior and Concomitant Medication Review	X	X	X	X	X	
Interventions						
Nivolumab Administration		X	X			
Ipilimumab Administration		X				
Surgery					X	
Clinical Procedures/Assessments						
Review Adverse Events	X	X	X	X		
Full Physical Examination	X	X	X	X	X	
Height	X					
Vital Signs and Weight	X	X	X	X	X	
ECOG Performance Status	X	X	X	X	X	
EORTC QOL C30	X			X		X
Surgeon Assessment	X			X		
Medical Oncology Assessment	X	X	X	X		
Laboratory Procedures/Assessments: analysis performed by LOCAL laboratory ^a						
Pregnancy Test – Urine or Serum β-HCG	X					
CBC with Differential	X	X	X	X		
Comprehensive Serum Chemistry Panel	X	X	X	X		
INR, PTT	X			X		
Urinalysis	X					
TSH (reflex T3, T4 if abnormal)	X	X		X		
Efficacy Measurements ^b						
Tumor Imaging with CT/MRI	X			X		
CA-125	X			X		
Circulating tumor cells	X			X		
Tumor Biopsies/Archival Tissue Collection/Correlative Studies Blood						
Laparoscopy for tissue and PCI score assessment	X					
Correlative Studies Blood Collection ^c	X	X		X	X	

a. Screening lab tests to be performed within 14 days before first dose. After Cycle 1, pre-dose lab procedures can be conducted <72 hours before dosing.
 b. For CT scans, scheduling window is +/- 7 days.
 c. Serum mesothelin and osteopontin will be obtained at the times of tumor imaging and upon tumor progression.

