7.13 Laboratory Procedures/Assessments

Details regarding specific laboratory procedures/assessments to be performed in this trial are provided below Laboratory Safety Evaluations (Hematology, Chemistry and Urinalysis) Laboratory tests for hematology, chemistry, urinalysis, and others are specified in Table 4.

Table 4. Laboratory Tests

Hematology	Chemistry	Urinalysis	Other
Hematocrit	Albumin	Blood	Serum β -human chorionic gonadotropin (β -hCG) †
Hemoglobin	Alkaline phosphatase	Glucose	PT (INR)
Platelet count	Alanine aminotransferase (ALT)	Protein	PTT
WBC (total and differential)	Aspartate aminotransferase (AST)	Specific gravity	Total triiodothyronine (T3)
Red Blood Cell Count	Carbon Dioxide (CO_2 or bicarbonate)	Microscopic exam (If abnormal results are noted)	Free thyroxine (T4)
Absolute Neutrophil Count	Calcium	Urine pregnancy test †	Thyroid stimulating hormone (TSH)
Absolute Lymphocyte Count	Chloride		Blood for correlative studies
	Glucose		
	Potassium		
	Sodium		
	Total Bilirubin		
	Total protein		

Hematology	Chemistry	Urinalysis	Other
	Blood Urea Nitrogen		

† Perform on women of childbearing potential only. If urine pregnancy results cannot be confirmed as negative, a serum pregnancy test will be required.

Laboratory tests for screening should be performed within 14 days prior to the first dose of treatment. After Cycle 1, pre-dose laboratory procedures can be conducted up to 72 hours prior to dosing. Results must be reviewed by the treating investigator or qualified designee and found to be acceptable prior to each dose of trial treatment.

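### Sections 4.4 and 6.6.2 classify some women differently for childbearing potential, and the 72-hour pregnancy-test criterion is not carried into Table 2 or Section 7.13, which apply a general 14-day window

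*Combined protocol and SAP*

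**What the plan says.** **Who is of childbearing potential.** Section 4.4, item 14b, states: "Subjects of childbearing potential are those who have not been surgically sterilized or have not been free from menses for > 1 year". It sets no age limit. It offers a woman in that group three ways to comply: two birth-control methods, surgical sterility or abstinence. For detail it refers to Section 5.8.2.

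Section 6.6.2 uses a different term, highly unlikely to conceive, and gives three routes to it: surgical sterilization; being postmenopausal, where a woman who is at least "45 years of age and has not had menses for greater than 1 year will be considered postmenopausal"; or being "not heterosexually active for the duration of the study". A woman who meets none of these may be enrolled only if she will use two methods.

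The footnote to Table 4 in Section 7.13 restricts pregnancy testing to women of childbearing potential, which is the 4.4 term.

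**When the test is done.** Under item 14a of Section 4.4, women of childbearing potential "should have a negative urine or serum pregnancy within 72 hours prior to receiving the first dose of study medication". Table 2 marks the pregnancy test in the Screening column (day -28 to -1) and not at C1 D1. Footnote a, attached to the heading of the laboratory block that contains the test, reads: "Screening lab tests to be performed within 14 days before first dose". Section 7.13 agrees with the footnote: "Laboratory tests for screening should be performed within 14 days prior to the first dose of treatment". Its Table 4 lists both the serum and the urine pregnancy test. Neither place makes an exception for 72 hours.

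Section 4.2 does not permit waivers of enrollment criteria.

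**The concern.** These passages decide who is tested for pregnancy before a first dose, who must use contraception, and when a test result is too old to count. Section 6.6.2 itself warns of possible harm to a fetus. If two sections sort the same woman differently, her obligations depend on which page the site opens. If the flow chart shows a longer window than the eligibility criterion, a coordinator who schedules from the flow chart can enroll a woman in breach of that criterion without noticing.

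**Working it through.** The plan gives no figure to reproduce here. The check compares the passages and counts cases.

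**1. Definitions.** Describe a woman by four yes/no facts: sterilized (S), more than 1 year without menses (A), aged 45 or over (O), not heterosexually active (H). That gives 2 × 2 × 2 × 2 = 16 profiles.

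- 6.6.2: able to conceive if not S, not (A and O), and not H. This covers 3 profiles.
- 14b, reading *or* as neither sterilized nor more than 1 year without menses: not S and not A. This covers 4 profiles.
- 14b, reading *or* literally: not S or not A. This covers 12 profiles.

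| Reading of 14b | Able to conceive in 6.6.2 only | In 14b group only | Discordant, of 16 |
|---|---|---|---|
| Neither/nor | 1 | 2 | 3 |
| Literal | 0 | 9 | 9 |

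The profiles are logical cases, not patients, so these counts are not frequencies.

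*Neither/nor reading.* The single profile in the first column is unsterilized, under 45, more than 1 year without menses and heterosexually active. For example, a 40-year-old with 13 months of amenorrhea is outside the 14a test and the 14b contraception rule, while 6.6.2 asks her for two methods. The other 2 profiles are women who menstruate, are not sterilized and are not heterosexually active. There 14b is the wider definition, and abstinence already satisfies it.

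*Literal reading.* The 9 profiles are:

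- sterilized, without more than 1 year of amenorrhea: 4
- unsterilized, with more than 1 year of amenorrhea, and either 45 or over or not heterosexually active: 3
- unsterilized, menstruating and not heterosexually active: 2

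Sterility or abstinence satisfies 14b for all but one of these. The exception is the unsterilized, heterosexually active woman of 45 or over with more than 1 year of amenorrhea. 14b asks her for two methods; 6.6.2 treats her as postmenopausal and does not.

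So under either reading exactly one profile receives contradictory contraception instructions. Under the first reading she is under 45, and under the second she is 45 or over.

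**2. Cross-reference.** Section 5 runs from 5.1 to 5.4, so Section 5.8.2 does not exist. The contraception text is in 6.6.2. A reader of 14b is not led to the passage that differs from it.

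**3. Windows.** 72 hours is 3 days, and 14 − 3 = 11. A test on about day -14 to -4 therefore meets footnote a and 7.13 and fails 14a. A test on day -3 to -1 lies inside 72 hours, inside 14 days and inside the Screening column, so it meets every passage. The windows nest: 72 hours within 14 days within 28 days.

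**The case against.** The strongest reply is that the documents can be followed without contradiction. 14a is a specific eligibility criterion, whereas the 14-day text is a general outer limit for all screening laboratory tests. Section 7.3 requires every criterion to be reviewed, and 4.2 bars waivers, so a day -14 pregnancy test simply fails eligibility. The Screening column runs to day -1, so the absence of a mark at C1 D1 is compatible with 72 hours. This stands. What remains is that the two places from which a site schedules the test do not show its tighter limit.

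On the definition, 6.6.2 neither uses the term childbearing potential nor sets a testing rule, and it makes its contraception requirement a condition of taking part. A site that applies both sections would still require two methods from the 40-year-old above. The literal reading also has support inside 14b: surgical sterility as a way to comply has content only if some sterilized women are in the group. These points limit the consequence but do not remove the mismatch, because the literal reading departs from 6.6.2 as well.

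Three stronger readings might be inferred, and the documents do not support them:

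- *That women able to conceive can generally start drug untested.* This arises for one profile, and only on the neither/nor reading. Read literally, 14b brings every woman whom 6.6.2 treats as able to conceive into the tested group.
- *That the protocol permits a test older than 72 hours.* Taken as a whole it does not.
- *That Section 4.7, item 6, is empty because no pregnancy test is scheduled after screening.* That item stops study treatment when "The participant has a confirmed positive serum or highly-sensitive urine pregnancy test". It acts on any such result and does not promise scheduled tests, and Section 7.1.2 allows unscheduled procedures. The absence of later tests is a monitoring choice, not a contradiction.

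**Conclusion.** The inconsistency is real and limited. Sections 4.4 and 6.6.2 disagree in 3 of 16 logical profiles on one reading of 14b and in 9 of 16 on the other. On each reading one profile receives contradictory contraception instructions. The cross-reference that should connect the two sections is dead. For the test window, 11 of the 14 days that the flow chart and 7.13 allow fall outside 14a. That creates a foreseeable risk of an eligibility violation, not a licence for one.

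The conclusion assumes that footnote a covers the pregnancy test, because the footnote is attached to the block in which the test is listed, and that the test in Table 4 falls under the 14-day sentence of 7.13. The documents do not give the number of women affected. The sample size and the primary analysis are unaffected. The correction is worth making because it concerns an eligibility and fetal-safety rule and costs almost nothing.

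**What to change.** Reconcile the passages:

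1. Use one definition of childbearing potential in 4.4 item 14b, 6.6.2 and the Table 4 footnote, worded so that *or* cannot be read two ways. State how age, amenorrhea, sterilization and sexual activity enter it, and whether the same definition governs both testing and contraception.
2. Correct the reference to Section 5.8.2 in 14b.
3. Give the pregnancy test its own footnote in Table 2 and its own sentence in 7.13, separate from the 14-day rule, so that its window is the same there as in 14a.

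Which definition and which window apply is for the investigator to decide.

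The cost is wording in five places (14b, 6.6.2, the Table 4 footnote, Table 2 and the text of 7.13). No visit is added, and the statistical analysis does not change.

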4.5 Subject Identification & Recruitment

Patients will be identified during the initial medical oncology or surgical oncology appointment. Patients will be screened for the appropriate inclusion and exclusion criteria and recruited to the trial as appropriate. There will be no use of advertisements, but it will be listed on the Cancer Center website. Patients will not be identified through medical records.

4.6 Location

This trial will be a single institution study. Recruitment of all patients will happen at the University of Chicago main site. Patients will undergo all interventions at the University of Chicago main site, but may receive the immunotherapy at the satellite sites.

4.7 Discontinuation of Study and Participant Withdrawal

Discontinuation of study intervention does not represent withdrawal from the study. As data on clinical events beyond study intervention discontinuation may be important to the study, they must be collected through the participant's last scheduled follow up, even if the participant has discontinued study intervention. Therefore, all participants who discontinue study intervention prior to completion of the protocol-specified treatment period will still continue to participate in the study.

Participants may discontinue study intervention at any time for any reason or be discontinued from the study intervention at the discretion of the investigator should any untoward effect occur. Also, a participant may be discontinued from study intervention by the investigator if study intervention is inappropriate, the study plan is violated, or for administrative and/or other safety reasons. A participant must be discontinued from study intervention but continue to be monitored in the study for any of the following reasons:

1. The participant or participant's legally acceptable representative requests to discontinue study intervention.
2. Any occurrence of another malignancy that requires treatment.
3. Unacceptable AEs or toxicities
4. The participant interrupts study intervention administration for >28 consecutive days
5. The participant has a medical condition or personal circumstance which, in the opinion of the investigator, placed the participant at unnecessary risk from continued administration of study intervention.
6. The participant has a confirmed positive serum or highly-sensitive urine pregnancy test.

A participant must be withdrawn from the study if the participant or participant's legally acceptable representative withdraws consent from the study. If a participant withdraws from the study, they will no longer receive study intervention or be followed at scheduled protocol visits.

Lost to Follow-up

If a participant fails to return to the clinic for a required study visit and/or if the site is unable to contact the participant, the following procedures are to be performed:

1. The site must attempt to contact the participant and reschedule the missed visit. If the participant is contacted, the participant should be counseled on the importance of maintaining the protocol-specified visit schedule.
2. The investigator must make every effort to regain contact with the participant at each missed visit (e.g. telephone calls and/or a certified letter to the participant's last known mailing address or locally equivalent methods). These contact attempts should be documented in the participant's medical record.
3. Note: A participant is not considered lost to follow-up until the last scheduled visit for the individual participant. The missing data for the participant will be managed via the prespecified statistical data handling and analysis guidelines.

5.0 TRIAL INTERVENTIONS

5.1 Pre-intervention Testing

Once consent is obtained, if not already performed patients will have a CT or MRI of the Abdomen and Pelvis and a CT of the Chest to determine extent of disease. They will also undergo a laparoscopy or mini-laparotomy for peritoneal carcinomatosis index (PCI) staging and pre-treatment tissue biopsy. The laparoscopic surgery is performed under general anesthesia, and involves inserting a 5 or 10 mm camera inside the peritoneal cavity to visually assess the peritoneal disease burden. Tissue biopsy is obtained by inserting a second 5 mm port and biopsying one or multiple areas of diseased peritoneum. Each biopsy site will be clearly marked by location for pathological identification. Patients with extensive prior surgery that precludes a safe laparoscopy could undergo a mini-laparotomy, in which a small incision is made to assess the burden of disease in the peri-incisional area. This laparoscopy or mini-laparotomy is standard of care for patients with peritoneal mesothelioma who are considered for CRS/HIPEC.

